## **Laboratory procedures**

The collected urine samples were transported to the China-Zanzibar Pathogen Biology Laboratory located in Pemba Island for analysis. In the laboratory, trained technicians performed urine filtration and microscopic

examination to detect *Schistosoma haematobium* eggs. The egg counts were manually recorded on paper by the technicians and subsequently entered into a Microsoft Excel database using a double-data-entry method to ensure accuracy.

### Recruitment and Training of CHVs

Six CHVs were recruited from local communities. To ensure the quality of the intervention, CHVs participated in a two-day training workshop led by public health experts. The training covered:

- **Basic knowledge of schistosomiasis:** Life cycle, transmission routes, clinical symptoms, diagnosis, and treatment.
- **Health education skills:** Effective use of educational materials (e.g., slides, videos, microscopes), communication techniques, and interactive teaching methods.
- **Practical training:** Microscopic observation of Schistosoma eggs and intermediate host snails, role-playing, and feedback sessions.
- **Assessment:** CHVs were evaluated through written tests and simulated teaching sessions. Only those who passed the assessment were allowed to participate in the intervention.

### Structured health education sessions

The 6-month intervention (February-August 2024) featured (Table 1):

Table 1 CBPR-Integrated Schistosomiasis structured health education sessions.

Session	Core Content	CEPEM Components	Duration	Framework Alignment
1	
Schistosomiasis life cycle & transmission
 
 
• Using local water source photos
 
• Analyzing common exposure behaviors (laundry, farming)
 
	
Community Embedding
 
 
• Culturally-grounded case studies
 
• Trust capital utilization
 
	2 hours	CHVs as Cultural Insiders

---

	Microscopic			
	observation of host			
	snails			
2	• Local snail specimens	Participatory Methodology	2.5 hours	Interactive Sessions
	• High-risk	• Hands-on learning		
	transmission zone			
	identification			
	Pathological impacts			
	on organs	Systems		
3	• Anatomical model demonstration	Reinforcement		Household-
	• Symptom self-check	• Household practice extension	2 hours	School Linkage
	forms			
	Prevention knowledge			
	games	Participatory		
4	• Schistosomiasis quiz	Methodology	1.5 hours	Peer-Led
	• Risk behavior simulation	• Peer-facilitated learning		Learning
	Preventive measures			
	poster exhibition	Systems		
5	• Safe water source guidelines	Reinforcement		Infrastructure
	• Hygiene practice visualization	• Infrastructure advocacy	2 hours	Advocacy
	Key message reinforcement	Community		
6	• Educational booklet distribution	Embedding		Trust Capital
		• Community	1 hours	Utilization
		resource mobilization		

---

---

- Core knowledge

- retention test

---

## Traditional Intervention

The control group schools A and B received traditional health education delivered by PHCs providers, following the standard health education practices recommended by the Ministry of Health Tanzanian, Tanzania. The health education content focused on general disease prevention and hygiene promotion, key topics included:

- Avoiding consumption of untreated water (e.g., “Do not drink untreated water from rivers, lakes, or ponds”).
- Promoting proper sanitation practices (e.g., “Do not defecate in open areas”).
- Encouraging safe recreational activities (e.g., “Avoid swimming or playing in cercaria-infested water bodies”).

## Statistical analysis

The data were double-entered into Microsoft Excel, systematically organized, coded, and verified for accuracy before being imported into IBM SPSS Statistics 26.0 for analysis. *S. haematobium* egg counts were stratified into light intensity (1–49 eggs/10 ml of urine) or heavy-intensity ( $\geq 50$  eggs/10 ml of urine) infection, based on WHO guidelines . For the KAP questionnaire: Knowledge scores were calculated based on correct responses (1 point per correct answer, maximum 10 points). Attitudes were evaluated using a 5-point Likert scale with a maximum score of 55 points. Behavioral patterns were scored according to frequency (1-3 points per item), totaling a maximum of 30 points. All scores were converted into percentage equivalents and categorized as "good" (80-100%), "moderate" (60-80%), or "poor" (<60%) . Satisfaction ratings were quantified with 1 point for "dissatisfied," 2 points for "neutral," and 3 points for "satisfied," yielding a maximum satisfaction score of 6 points.

Demographic and KAP data were analyzed descriptively: continuous variables were expressed as Mean  $\pm$  SD (normally distributed) or median [IQR] (non-normal). A two-way repeated-measures ANOVA with Bonferroni correction assessed temporal

effects (baseline/post-intervention/follow-up) and group differences. For ordinal data violating ANOVA assumptions (normality/homoscedasticity via Q-Q plots/Levene's test), the Kruskal-Wallis test was applied.

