# **Health Education Model Led by Community Health Volunteers**

**NCT06312462**

**24-August-2025**

## **Study Protocol and Statistical Analysis Plan**

### **Study Design and Sampling**

A repeated cross-sectional design compared the impact of CHVs-led (CBPR-based) health education versus traditional health education on schistosomiasis-related KAP over 12 months (February 2024 - February 2025). The CBPR approach included: (1) Needs assessment using baseline surveys; (2) Co-design of interventions with community stakeholders; (3) Implementation led by trained CHVs; and (4) Mixed-methods evaluation combining infection rates and questionnaires(Figure 1). The process emphasized cultural adaptation, community ownership, and continued improvement to ensure sustainable interventions.

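### Does the shared 80% edge of the 'good' and 'moderate' KAP bands require a change to the plan?

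*Combined protocol and SAP*

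**What the plan says.** The Statistical analysis section defines three integer scores. Knowledge is "1 point per correct answer, maximum 10 points". For attitude, "Attitudes were evaluated using a 5-point Likert scale with a maximum score of 55 points". For behaviour, "Behavioral patterns were scored according to frequency (1-3 points per item), totaling a maximum of 30 points".

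The banding follows: "All scores were converted into percentage equivalents and categorized as" good, moderate or poor, with the limits "good' (80-100%), 'moderate' (60-80%), or 'poor' (<60" per cent. The conversion formula is not given, and no other section says where exactly 80% goes.

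In the same paragraph the infection bands do not overlap: "light intensity (1–49 eggs/10 ml of urine) or heavy-intensity", with heavy starting at 50 eggs. The section then describes KAP data by mean and SD or median and IQR. For inference it uses a two-way repeated-measures ANOVA, with Kruskal-Wallis as the alternative for ordinal data that break the ANOVA assumptions.

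**The concern.** The figure 80 ends one band and begins the next. On a 10-item knowledge test, 8 correct is a common score, so this is not a point that data rarely reach. Two analysts following the printed text could place the same pupil in different bands and report different shares of 'good' and 'moderate'.

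Using one rule for every school and survey would not remove the effect from a comparison of 'good' shares, because the fraction of pupils at exactly 80% changes as scores rise. Timing adds to the worry. The study ran "over 12 months (February 2024 - February 2025") and the document is dated August 2025, so a rule left unwritten could in principle be settled after the shares were known. At stake is whether the descriptive band percentages can be reproduced from the plan alone.

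**Working it through.** **Inputs.** The scale maxima of 10, 55 and 30 and the band limits come from the Statistical analysis section. The percentage formula is an assumption: score / maximum × 100, the natural reading because only maxima are stated. Item counts are inferred: 55/5 = 11 attitude items (range 11 to 55 if coded 1 to 5) and 30/3 = 10 behaviour items (range 10 to 30). The plan states no figure to reproduce here.

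**Step 1: can 80% occur?**

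| Scale | 80% of maximum | Attainable? | 80% if rescaled from minimum to maximum | Attainable? |
|---|---|---|---|---|
| Knowledge | 0.8 × 10 = 8 | yes | 8 | yes |
| Attitude | 0.8 × 55 = 44 | yes | 11 + 0.8 × 44 = 46.2 | no |
| Behaviour | 0.8 × 30 = 24 | yes | 10 + 0.8 × 20 = 26 | yes |

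The overlap reaches all three scales under score over maximum, and two of the three under the alternative formula.

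**Step 2: which edges are open?** At 60% (6, 33 and 18 points) the score is not 'poor', because that band is strictly below 60%. It falls in 'moderate', the band whose range begins there. Only the 80% edge is open, and carrying the 60% rule upward assigns 80% to 'good'.

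**Step 3: how many pupils could sit on the edge?** The documents give no score distribution, so everything in this step is illustrative. For knowledge, let p be the average proportion correct. With 10 independent items and one p for all pupils, P(X = 8) = 45 p⁸(1 − p)². The last column lets pupils differ (beta-binomial, within-pupil correlation 0.2).

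| p | P(X = 8), independent | P(X = 8), correlation 0.2 |
|---|---|---|
| 0.5 | 4.4% | 9.4% |
| 0.6 | 12.1% | 13.1% |
| 0.7 | 23.3% | 15.5% |
| 0.8 | 30.2% | 15.0% |

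At p = 0.7 the 'good' share is 38.3% if 80% counts as 'good' and 14.9% if not (independent items), or 49.1% and 33.6% with correlation 0.2.

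For the other scales, using a normal approximation over a one-point interval, the share at exactly 44 of 55 is 4.4% to 9.9% (mean 40 to 46, SD 4 to 8). The share at exactly 24 of 30 is 5.5% to 13.2% (mean 20 to 26, SD 3 to 5).

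**Step 4: would a difference between schools in 'good' share move?** The difference is P(X ≥ 8) under one coding and P(X ≥ 9) under the other.

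| p in the two schools | Independent: 80% 'good' / 'moderate' | Correlation 0.2: 80% 'good' / 'moderate' |
|---|---|---|
| 0.5 vs 0.7 | 33 / 14 points | 29 / 23 points |
| 0.6 vs 0.8 | 51 / 33 points | 34 / 32 points |
| 0.7 vs 0.9 | 55 / 59 points | 36 / 42 points |

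The large shifts come from assuming that every pupil has the same chance of a correct answer, which is unrealistic for pupils aged 8 to 16. Letting pupils differ leaves shifts of about 2 to 6 points, in either direction.

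**Step 5: does the edge enter an analysis?** Means, medians and an ANOVA on scores use the score itself, so the coding of 80% leaves them unchanged. The plan specifies no endpoint, test or between-school comparison based on band shares. Step 4 therefore measures a contrast that the plan does not call for.

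**The case for a change.** The best case for a change is that it costs one sentence. The printed 'moderate' range does include 80%, and reading the edge as lower-inclusive is an inference from how 60% is handled. The egg-count bands show that the authors could write a closed boundary when they chose to. If 80% was already coded 'good', stating so alters nothing; if not, the reader should know.

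There is also a possible route into a test. The Kruskal-Wallis fallback is for ordinal data, and the section does not say whether that means the scores or the bands. If it means the bands, the coding of 80% would enter a p-value.

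Most of this stands as description: the overlap is literal, the formula is unstated, and a careful author would have written the edge differently. Two parts do not carry far. The two readings are not equally supported, because the only closed edge on this scale points to 'good'. And nothing in the text directs Kruskal-Wallis to the bands, so that route is a possibility and not a stated analysis.

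**Conclusion.** The overlap at 80% is a genuine looseness of wording, but it is a gap that an analyst fills sensibly, and no change to the plan follows. The likely intent, 80% as 'good', can be read from the treatment of 60%. A written rule to that effect would probably change no number.

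The reach is limited to the descriptive shares in two adjacent bands. Under assumed distributions the affected fraction could be about 4% to 30% of pupils on knowledge, 4% to 10% on attitude and 6% to 13% on behaviour. Those shares would be wrong only if the analyst had departed from the visible convention, and nothing in the documents suggests that.

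This rests on three assumptions: percentages are score over maximum (otherwise attitude may not be affected at all), the ANOVA and its fallback are run on scores, and no inference is drawn from band shares.

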### **Cluster Sampling Implementation**

A three-stage cluster sampling method was implemented:

1. School selection: Three public primary schools were randomly selected from distinct geographical regions of Pemba Island, matched for demographic characteristics (student population, gender ratio, and age distribution).
2. Cluster formation: Within each school, grades 4–6 (ages 8–16 years) were designated as natural clusters, reflecting the target population exposed to schistosomiasis transmission.
3. Participant inclusion: All students meeting eligibility criteria within selected grades were enrolled, minimizing selection bias through complete enumeration within clusters.

Intervention allocation:

- Intervention group: One school received CBPR-based education led by CHVs.

- Control group A and B: Two schools received standard health education from PHCs providers.

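### The KAP group comparisons adjust for no pupil characteristics, although no random allocation of the three schools is described and pupils span ages 8–16

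*Combined protocol and SAP*

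**What the plan says.** The Statistical analysis section opens its account of methods with "Demographic and KAP data were analyzed descriptively". It then names one inferential model: "A two-way repeated-measures ANOVA with Bonferroni correction assessed temporal" "effects (baseline/post-intervention/follow-up) and group differences". For ordinal data that fail the ANOVA assumptions, "the Kruskal-Wallis test was applied". These are the only inferential methods in the document. Age, sex and grade appear in none of them, and no section mentions analysis of covariance, regression, a mixed model or a stratified comparison.

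Under Cluster Sampling Implementation, three schools are chosen at random from different regions and are "matched for demographic characteristics (student population, gender ratio, and age distribution"). All eligible pupils in grades 4–6 are enrolled. The allocation is then listed: "Intervention group: One school received CBPR-based education led by CHVs" and "Control group A and B: Two schools received standard health education from PHCs providers". How the intervention school was picked from the three is not stated.

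The Eligibility Criteria admit ages 8–16. They require consent, assent and at least two years' residency, and they exclude pupils with incomplete questionnaires. The Study Design and Sampling section calls the design repeated cross-sectional.

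**The concern.** Age, grade and sex plausibly predict what a pupil knows about schistosomiasis and how the pupil behaves around water. Where chance has not been shown to balance the groups, a difference in pupil mix between schools passes straight into an unadjusted group difference. The plan has the data to deal with this: age and grade must be known for each pupil to establish eligibility, and the analysis section refers to demographic data. It plans no use of them beyond description.

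At stake is whether a difference in KAP scores between the CHV-led school and the control schools could partly reflect who was surveyed. The repeated cross-sectional label adds a second route: if pupils are sampled afresh, the mix within a school may change from wave to wave.

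**Working it through.** The plan states no sample size, power, standard deviation or effect size, so it offers no figure to reproduce. The check is a reading of the text, followed by an illustration on assumed inputs.

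**1. Does any planned analysis adjust?** The ANOVA has time (three waves) and group. Kruskal-Wallis compares groups and takes no covariates. No other section supplies an adjusted or stratified analysis. The sentence quoted as "Demographic and KAP data were analyzed descriptively" does not itself say that demographics are used only for description, since it says the same of the KAP data, which are then tested. The conclusion rests on the absence of any other planned use.

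**2. Which contrasts are exposed?** Write the expected mean score in group g at wave t as the true group-and-wave mean plus s × G(g,t), where G is the mean grade of the pupils analysed and s is the score slope per grade.

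- Group difference at one wave, which is also what Kruskal-Wallis addresses: bias = s × [G(intervention) − G(control)]. The group main effect carries the average of this over waves.
- Change in one group minus change in the other: bias = s × {[G(int, later) − G(int, baseline)] − [G(con, later) − G(con, baseline)]}. If the same pupils are followed and G is their baseline grade, each bracket is zero and the additive effect cancels.
- Same pupils, but a slope that changes from s₀ to s₁ because older pupils learn at a different rate: bias = (s₁ − s₀) × [G(int) − G(con)], which does not cancel.

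The same reasoning applies to age and sex. The analysis section does not name the group-by-time interaction as its target, so the exposed contrasts cannot be set aside.

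**3. How large could it be?** Assumed inputs, neither from the documents: s = 3 to 8 percentage points per grade, and a gap in mean grade (between schools, or between waves within a school) of 0.2 to 0.4.

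- Low end: 3 × 0.2 = 0.6 points.
- High end: 8 × 0.4 = 3.2 points.

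To see what a gap of 0.4 requires, start from equal thirds in grades 4, 5 and 6 (mean 5.0). A mix of about 13%, 33% and 53% gives 4 × 0.133 + 5 × 0.333 + 6 × 0.533 ≈ 5.4. That is a substantial imbalance for matched schools with full enrolment, so the upper end is demanding.

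**4. Against the raw scales.** The maxima are 10 for knowledge, 55 for attitudes and 30 for behaviour. If percentages are score over maximum, one raw point is 10%, 1.8% and 3.3% respectively. The whole range of 0.6–3.2 is below one raw point on knowledge and behaviour. On attitudes the upper end is 3.2 × 55/100 ≈ 1.8 raw points.

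**The case against.** The strongest reply is that the design already does much of the work. Schools were matched on gender ratio and age distribution, the same three grades were taken everywhere, and every eligible pupil was enrolled. If the same pupils were followed, a repeated-measures contrast of change removes stable differences. With one intervention school, the school itself is the main confounder, and pupil covariates cannot touch that.

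Most of this stands, and it limits the size of the problem. It does not remove it. Grade is not a listed matching variable. The pupils analysed are those who consented, met the residency rule and returned complete questionnaires, so their mix can depart from the matched profile. Cancellation needs the same pupils and a change contrast; the plan's design label points away from the first, and its text does not specify the second.

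A reader might infer several stronger things that the documents do not support:

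- That allocation was non-randomised. The text is silent on how the intervention school was chosen; the most that can be said is that no random allocation is described.
- That matching was on whole-school figures. The text does not say whether the age and gender profiles refer to the school or to grades 4–6.
- That imbalance would push pupils across the 60% and 80% category limits. A different mix changes no pupil's score; it changes means and category proportions.
- That adjustment is worth a fixed percentage of extra pupils. The usual factor 1/(1 − R²) applies to independent between-pupil contrasts. It does not apply to a within-pupil change or to between-school variation.

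**Conclusion.** The concern holds in a limited form. The planned inferential methods contain no covariates and nothing else in the document supplies adjustment, in a three-school comparison with no described random allocation and a wide age range. Residual imbalance in age, sex or grade can bias the group main effect and the Kruskal-Wallis comparison. It can bias the group-by-time contrast if the pupil mix shifts between waves or if learning depends on these characteristics. If the same pupils are followed, additive fixed traits cancel from that contrast.

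The size cannot be derived from the documents. Under the assumed slopes and gaps it is 0.6–3.2 percentage points on the mean score, and smaller if matching carried through to the pupils analysed. The documents do not show that any imbalance occurred. This is a worthwhile, inexpensive improvement, secondary to the limit set by having one intervention school.

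**What to change.** Analyse each KAP score with a regression or mixed model containing group, wave, group-by-wave, age, sex and grade. If age and grade prove collinear across three consecutive grades, keep one of them. If the same pupils are followed, add covariate-by-wave terms, since the main effects of fixed traits do not alter the change contrast. Report the unadjusted contrast beside the adjusted one, tabulate age, sex and grade by school and wave, and keep Kruskal-Wallis as a descriptive check.

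The analysis section classifies egg counts by intensity but names no test for infection. If infection is to be compared between groups, specify a logistic model with the same terms.

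The cost is a short addition to the analysis section and a little more analysis work. Age and grade are needed for eligibility, and the plan refers to demographic data; sex is assumed to be among them. The named software can fit these models. There is one drawback: the document is dated 24 August 2025, after the February 2025 follow-up, so the adjusted model cannot be shown to be pre-specified and should be labelled as an added analysis. The report should also say that adjustment removes only measured pupil-level confounding, so that it does not lend the school comparison more credibility than one intervention school can support.

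### The Bonferroni family is undefined, no contrast that tests the programme is named, and nothing covers the three KAP scores

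*Combined protocol and SAP*

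**What the plan says.** The aim, under Study Design and Sampling, is a two-way comparison; the study "compared the impact of CHVs-led (CBPR-based) health education versus traditional health education on schistosomiasis-related KAP over 12 months". Cluster Sampling Implementation gives three schools: "Intervention group: One school received CBPR-based education led by CHVs" and "Control group A and B: Two schools received standard health education from PHCs providers". Whether A and B are analysed as two group levels or pooled is not stated.

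Statistical analysis defines three separate scores. Knowledge is marked out of 10 and behaviour out of 30, and between them stands the attitude score: "Attitudes were evaluated using a 5-point Likert scale with a maximum score of 55 points". None is named as primary.

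The only sentence on multiplicity reads "A two-way repeated-measures ANOVA with Bonferroni correction assessed temporal" and continues "effects (baseline/post-intervention/follow-up) and group differences". It gives no significance level, no number of comparisons, no group-by-time interaction or other programme contrast, and no rule spanning the three scores. If ANOVA assumptions fail for ordinal data, a Kruskal-Wallis test is substituted.

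**The concern.** The question is whether KAP improved more under CHV-led education than under traditional education. With a baseline and later waves, that is a difference in change between arms. The text names time effects and group differences. Neither is that contrast: a time effect can appear in all schools alike, and a group difference can already exist at baseline.

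Two things are then left open. First, knowledge, attitude and behaviour give three routes to one claim, and no hierarchy or adjustment covers them. Second, with three labelled schools and three waves, a Bonferroni family could be as small as three pairs or much larger. It could include comparisons that say nothing about the programme, such as A against B, and these would tighten the threshold for the ones that do. Nor is there a rule for a result that is significant against one control school but not the other. A reader of the results could not tell which comparison carries the conclusion or at what error rate.

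**Working it through.** The documents give no significance level, power, sample size or familywise error, so there is no stated figure to reproduce.

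**Inputs from the documents:** three scores, three waves, one programme school, two control schools.

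**Assumptions:** two-sided alpha 0.05; success on any one score; valid pupil-level tests; correlation between the three test statistics from 0 to 0.9; 80% unadjusted power as a reference point.

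**Reading 1: one unadjusted decisive test per score** (for example an interaction F test).

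- Independent scores: 1 − (1 − 0.05)³ = 1 − 0.857 = 14.3%; upper bound 3 × 0.05 = 15%.
- Correlated scores, by simulation: 13.6% at 0.3, 12.5% at 0.5, 10.9% at 0.7, 8.4% at 0.9.
- Other alphas, independent: 3.0% at 0.01 and 27.1% at 0.10.

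**Reading 2: the decisive tests are Bonferroni-adjusted pairs within each score.** With m comparisons in the family and r of them bearing on the programme, the any-of-three error under independence is 1 − (1 − 0.05/m)^(3r). Power is Φ(1.960 + 0.842 − z), where z is the two-sided critical value at 0.05/m.

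| Family per score | m | r | Per-test level | Any-of-three error | z | Power |
|---|---|---|---|---|---|---|
| School pairs | 3 | 2 | 0.0167 | 9.6% | 2.394 | 66% |
| School pairs × 3 waves | 9 | 4 | 0.0056 | 6.5% | 2.773 | 51% |
| The 9 above plus 9 within-school wave pairs | 18 | 4 | 0.0028 | 3.3% | 2.991 | 42% |

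Here r = 2 counts the CHV school against A and against B once; r = 4 counts both at the two post-baseline waves.

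One variant gives a higher error. If the three school pairs are a separate family at each wave, and success on any score against either control at either later wave counts, there are 3 × 2 × 2 = 12 routes at 0.0167 (bound 20%). Simulation, with equal schools and correlations of 0 to 0.7 between scores and 0 to 0.5 between waves, gives 13% to 17%, or 7% to 9% counting only results that favour the CHV school.

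**After the fix.** With all three null hypotheses true, Holm's familywise error equals that of Bonferroni at 0.05/3 = 0.0167: 1 − (1 − 0.0167)³ = 4.9% if independent, and 4.8%, 4.5%, 3.9% and 3.0% at correlations 0.3, 0.5, 0.7 and 0.9.

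**What these figures leave out.** The stated analysis has no term for school. As an illustration, take 100 pupils per school and an intraclass correlation of 0.01, both assumed. The design effect is 1 + 99 × 0.01 = 1.99. A nominal 5% test then has size 2 × [1 − Φ(1.960/√1.99)] = 16.5%, and any-of-three is about 42%.

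**The case against.** A reader might infer three stronger things, and the documents do not support them.

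*That the Bonferroni family includes A against B and within-school changes.* The text lists no such tests. They are a plausible result of default post hoc output with three schools, but if A and B are pooled there is one group pair and no A-against-B comparison. What is documented is an undefined family, not a wrongly composed one.

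*That a programme claim has a 14% false-positive rate.* That figure needs an alpha of 0.05, an any-one-score rule and independent scores, none of which is stated. The three scores come from the same pupils, so positive correlation is likely and the rate would be lower.

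*That the plan suffers both the 14% error and the power loss.* The 14.3% applies when the decisive test is unadjusted; the 66% and 51% apply when it is adjusted. They describe different readings. The separate-family-per-wave variant does combine raised error with 66% power, but it is one further reading with its own success rule, and the text does not select it.

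It is also fair to say that, read literally, time and group have at most three pairs each. The per-test level is then 0.0167, the same as Holm's strictest step, so the power cost is no greater than that of the fix at that step. The 80% starting point is arbitrary because the plan gives no power.

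What stands is that the text does not settle which of these readings applies, and the error rate and power depend on it.

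**Conclusion.** The concern holds in a limited, conditional form. The plan does not define its Bonferroni family, does not name the contrast that answers its own question, and has no primary score or adjustment across the three KAP outcomes.

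The size depends on the reading: up to about 14% nominal familywise error if each score is tested unadjusted at 0.05 and any one suffices; or, if adjusted pairs are decisive, about 3% to 10% on most readings, with power falling from 80% to 66% (three pairs) or 51% (nine). All of these are pupil-level figures and assume valid tests. With one programme school against two control schools the true error of a programme claim could be far higher, and defining the family does not cure that.

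**What to change.** For each KAP score, make the decisive test one contrast: the change from baseline to August 2024 in the CHV school minus the average change in schools A and B. Apply Holm across the three scores, or name one primary score. State the alpha. Keep A against B and within-school changes outside the confirmatory family and report them as estimates with confidence intervals. Report all three scores whatever their results.

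Using both controls removes the question of significance against one but not the other. With equal schools and equal variances it also gives a variance proportional to 1/n + 1/(2n) = 1.5/n, rather than 2/n against a single control school.

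Three points need wording alongside this:

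- Whether change is measured within pupil, since the design is called repeated cross-sectional while the analysis is repeated-measures.
- How the contrast is tested if ANOVA assumptions fail, because a Kruskal-Wallis test does not estimate it.
- What status the February 2025 results have. Several choices are acceptable; the text should state one.

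The document is dated August 2025, after the last survey in February 2025, and describes the analysis in the past tense. If the analysis has been run, the contrast must be labelled post hoc.

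The cost is analysis work and wording, a stricter threshold for each KAP score, and loss of confirmatory status for pairwise school and within-school tests. The text should also say that this controls nominal pupil-level error only and does not address one programme school against two control schools.
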